## 13.5 Secondary and Exploratory Objectives and Analysis Plans

### 13.5.1 Secondary endpoints (efficacy)

1. Oncotype DCIS-Score (validated RT-PCR assay for 12 genes). We expect that changes in this Score will be non-inferior in the gel arm.
2. Breast tissue and plasma levels of TAM and its metabolites [N-desmethyl tamoxifen (NDT), (E) and (Z) isomers of 4-hydroxytamoxifen (4-OHT), N- desmethyl-4-hydroxytamoxifen (Endoxifen)]. We expect that plasma levels will be different between arms, with higher levels in the oral arm but tissue levels will be similar between arms.
3. Ki67 LI in terminal duct lobular units, evaluated in the same manner as the primary endpoint (KI67 LI in the DCIS lesions). We expect that reduction in TDLU Ki67 LI will be non-inferior in the gel arm.

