## **2.2 Study Agent: 4-hydroxytamoxifen (4-OHT) transdermal gel formulation**

A potential alternative to oral tamoxifen is suggested by studies going back to the 1980s, which showed that 4-OHT, the monohydroxy metabolite of oral tamoxifen, has a far greater affinity for the estrogen receptor  $\alpha$  (ER) and is more effective than TAM in suppressing breast cancer cell growth [21]. Furthermore, 4-OHT has been shown to inhibit the growth of normal human breast cells [22], and cancerous cell lines in tissue culture with two-log greater potency than tamoxifen [23-25]. 4-OHT has approximately 100 times the potency of TAM in reducing proliferation of breast cancer cells *in vitro* [21]. Its binding affinity to ER is similar to estradiol (E2) and 25-to-50 times higher than tamoxifen [26]. Its efficacy in modulating ER expression is similar to the other major TAM metabolite, endoxifen [27]. However, 4-OHT has little activity when delivered orally, due to its rapid conjugation and inactivation by the liver. Additionally, plasma concentrations of 4-OHT are only about 2% of the parent drug levels [28]. The recognition by Mauvais-Jarvis et al. in 1986 that transdermal administration of 4-OHT may be possible, led to a study where *trans*-[H]-4-OHT (9 women) and *trans*-[H]TAM (3 women) was applied to the skin of the breast and tumor samples were obtained prior to, and 12 hours to 7 days following application [29]. Serial blood and urine samples were also collected. The results showed significantly greater retention of 4-OHT in breast tissue than TAM and appearance of TAM metabolites in the plasma, but little evidence of 4-OHT metabolism in the breast. These findings led the authors to hypothesize that 4-OHT may be a suitable compound for transdermal delivery in women with benign breast problems, where local delivery and avoidance of systemic toxicity are the goals. The same may be said for primary and secondary breast cancer prevention in unaffected high risk women and those with pre-invasive malignancy.

Pharmacokinetics and metabolism: 4-OHT is found in all tissues examined after administration of oral TAM and, along with endoxifen, is believed to be responsible for a major part of the anti-cancer efficacy of tamoxifen *in vivo* [30]. The concentrations of 4-OHT in breast tumor tissue are generally higher than

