simultaneous concentrations in normal breast tissue, and there is minimal metabolism in the breast, where tissue levels are stable for 2 days and detectable for 7 days [29]. At transdermal doses of 1, 2, and 4 mg daily, plasma levels of 4-OHT were 0.05, 0.13, and 0.2 ng/mL respectively, and were thus approximately 1/30 to 1/12, and 1/6 respectively, of those seen after 20 mg of oral TAM [31]. Metabolism of 4-OHT occurs in the liver. Clinically significant adverse effects of topical 4-OHT have not been reported to-date at the doses that have been studied (0.25 mg/day, 0.5 mg/day, 1 mg/day, 2 mg/day, and 4 mg/day). In addition, the topical application of 4-OHT may circumvent one source of tamoxifen resistance: the failure of women with CYP2D6\*4 polymorphisms to achieve sufficient levels of the active metabolites of tamoxifen when the agent is delivered orally [32, 33]. Together, these considerations provide strong rationale for testing 4-OHT in women with non-invasive breast cancer and those at increased risk of breast cancer.

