### **5.1 Dose Regimen and Dose Groups**

Experimental Arm: (Group 1)

4-hydroxytamoxifen gel applied to both breasts (2mg/breast) daily

Oral placebo taken daily

4 to 10 weeks of treatment between randomization and surgical resection

Control Arm: (Group 2)

Placebo gel applied to both breasts daily

20mg oral tamoxifen taken daily (taken as one 20mg capsule)

4 to 10 weeks of treatment between randomization and surgical resection

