- Drug concentration assays (only for study visit 1): 1) Fresh benign tissue 1x1x1 cm fragments (weight of each fragment is usually 200mg~300mg) from locations defined in **Figure 2**, from surgical cavity, to avoid interfering with margin assessment on the main specimen. The 1x1x1 cm breast tissue sample will be split in half, and a slice of tissue about 3 mm thick, (see Figure 2A, bottom right panel, piece B in red) will be taken from one face, and placed in formalin for at least 6 and at most 72 hours, then embedded in paraffin. The remainder (piece A in yellow) of the fresh breast sample will be flash-frozen for drug assay. 2) An aliquot of plasma from the research blood sample drawn with a 10 mL Lavender top tube (K2EDTA) at the Day of Surgery (study visit 1) will be to obtain plasma for measurement of circulating drug concentrations. Measurement of drug metabolites (tamoxifen, N-desmethyltamoxifen, E and Z isomers of both 4-OHT and endoxifen) (see the session 7.1, the schedule of event table footnote #9 for details). These fresh frozen tissue samples along with the paraffin block (Sample B in Figure 2), plasma, and buffy coat samples will be sent as a single shipment for each participant (frozen samples on dry ice) to NU from participating sites. FFPE blocks will be shipped in cold condition. At NU-PCF, the Sample B FFPE will be sectioned and stained with H&E to determine the tissue composition of the drug concentration sample. The histology findings from this research sample will not be reported back to clinical teams.

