### 13.5.4 Analysis Plan for Secondary Endpoints:

Secondary outcomes will be summarized by

treatment arm using descriptive statistics, including mean and confidence interval, or median and interquartile range for continuous outcomes, and proportions and confidence intervals for categorical variables. Outcomes will be compared between arms, with two main types of analyses being conducted: noninferiority testing and testing for differences between arms, depending on the specific hypotheses for each outcome. **Noninferiority analyses.** Similar to the primary outcome, we expect changes in secondary efficacy outcomes (Oncotype DCIS-Score) to be similar (noninferior) in the 4-OHT gel arm vs. oral tamoxifen arm. Because preliminary data necessary for setting noninferiority margins are not available for all endpoints, we will use a strategy similar to how the non-inferiority margin was set for the primary endpoint, i.e. we will set the margin  $M$  to correspond to a 35% change from the average baseline value observed among all patients (i.e. pooling across both study arms). These biomarkers will be compared between arms using ANCOVA models similar to those described for the primary endpoint, with post-treatment measurement as the outcome variable, and with treatment arm and baseline value as predictors, and testing  $H_0: \gamma \geq M$  vs.  $H_1: \gamma < M$  as described above. **Treatment differences.** Continuous endpoints for which treatment differences are expected post-treatment (breast and plasma levels of TAM and its metabolites; plasma proteins involved in coagulation; plasma markers of systemic estrogenic effect; and BESS questionnaire) will be compared between arms using a two-sample t-test. Normality assumption will be checked, and data may be transformed (e.g. logarithmically) to satisfy the normality assumption. If no suitable transformation can be found, groups will be compared using the Wilcoxon ranksum test. Additional exploratory analyses will include linear regression models and will adjust for additional covariates. Outcomes for which changes are expected to be different between arms will be analyzed using ANCOVA models as described for the primary endpoint, but testing whether the treatment effect is 0 rather than the non-inferiority margin  $M$ , i.e.  $H_0: \gamma = 0$  vs.  $H_1: \gamma \neq 0$ . These tests will be two-sided. Tests of these pre-specified hypotheses will not be adjusted for multiple comparisons, and will be interpreted accordingly.

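### Sections 13.5.1 and 13.5.4 contradict each other on whether tissue drug levels should be similar between arms, and the planned difference test could not establish similarity even for 4-OHT

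*Combined protocol and SAP*

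**What the plan says.** Section 13.5.1, item 2, names tamoxifen, NDT, (E)- and (Z)-4-OHT and endoxifen as one endpoint. It expects plasma levels to differ, "with higher levels in the oral arm but tissue levels will be similar between arms". The sentence applies to the whole list.

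Section 13.5.4 sorts secondary endpoints into a non-inferiority group and a group where the arms are expected to differ. It puts "breast and plasma levels of TAM and its metabolites" in the second group. The test is a two-sample t-test, with transformation if needed and a Wilcoxon rank-sum test if no transformation works. No margin is given for tissue levels.

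Section 5.1 defines the gel arm as "4-hydroxytamoxifen gel applied to both breasts (2mg/breast) daily" plus "Oral placebo taken daily". Section 2.2 says of 4-OHT that "there is minimal metabolism in the breast". The same section says that 4-OHT, "along with endoxifen, is believed to be responsible for a major part of the anti-cancer efficacy of tamoxifen", and adds: "Its efficacy in modulating ER expression is similar to the other major TAM metabolite, endoxifen".

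The analytes are assayed one by one. Section 10.2.1 has "Measurement of drug metabolites (tamoxifen, N-desmethyltamoxifen, E and Z isomers of both 4-OHT and endoxifen". Section 2.3.3 gives the purpose: to learn whether transdermal delivery reaches effective concentrations in breast tissue. None of Sections 1.2, 2.3.3, 8.2, 10.2.1, 13.5.1 or 13.5.4 names a key analyte or a combined measure for tissue.

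**The concern.** The hypothesis and its analysis point in opposite directions. One section predicts similarity for five analytes. The other plans to look for a difference in the same five.

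For tamoxifen and NDT the prediction of similarity is not plausible on the protocol's own account of what the gel arm receives. A difference there is foregone and says nothing about delivery. For 4-OHT, where similarity is plausible, the planned test can only find a difference or fail to find one, and failing to find one is not evidence of similarity.

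At stake is how the endpoint will be reported. A non-significant p-value for tissue 4-OHT could be written up as similar tissue levels, and then as matched active drug, although the protocol credits endoxifen with part of the activity.

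**Working it through.** **1. Analyte by analyte, from the text.**
- Tamoxifen and NDT: the gel arm gets 4-OHT and a placebo capsule. Section 2.2 describes 4-OHT as a metabolite of tamoxifen, so tamoxifen lies upstream of the drug given. Similarity is not plausible.
- Endoxifen: Section 2.2 reports little 4-OHT metabolism in the breast but says that the liver metabolises it. The gel-arm level is not settled by the documents.
- (Z)- and (E)-4-OHT: similarity is plausible and is the question of interest.

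**2. The plan's own figure.** Section 2.3.2 gives (Z)-4-OHT in breast adipose tissue in the previous DCIS trial (NWU 07-9-02) as 5.4 ± 2.8 ng/g (oral) and 5.8 ± 9.3 ng/g (gel), p = 0.88, and calls the groups equivalent. The number per arm is not stated; 28 women enrolled and 18 were evaluable for the primary endpoint. I read ± as SD and assume equal arms. Welch's test gives p = 0.904 at 9 per arm, 0.884 at 13 and 0.880 at 14, so 0.88 is reproduced at about 13 to 14 per arm. If ± were a standard error, z = 0.4/√(2.8² + 9.3²) = 0.041 and p = 0.97, which does not fit.

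The 95% interval for gel minus oral is −5.1 to +5.9 ng/g at 14 per arm and −6.9 to +7.7 at 9. That is about ±100% of the oral mean, or wider. A p-value of 0.88 here does not show equivalence.

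**3. The planned trial, raw scale.** Section 3.2 gives 45 per arm for study endpoints; Section 13.2 gives 80 to 90 women in all, so 40 to 45 per arm. Standard error = √((2.8² + 9.3²)/n).
- n = 45: √(94.33/45) = 1.448. The 95% half-width is 2.91 ng/g, or 54% of 5.4.
- n = 40: √(94.33/40) = 1.536. The half-width is 3.09 ng/g, or 57%.
- Power to detect a halved gel-arm level (difference 2.7, SDs unchanged, two-sided 5%): Φ(2.7/1.448 − 1.96) = 46% at 45 per arm; Φ(2.7/1.536 − 1.96) = 42% at 40.

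**4. The same inputs, log scale (log-normality assumed).** Log SD = √ln(1 + CV²): 0.488 for oral (CV 2.8/5.4) and 1.128 for gel (CV 9.3/5.8).
- n = 45: standard error √((0.488² + 1.128²)/45) = 0.183. Power to detect a halving is Φ(0.693/0.183 − 1.96), about 97%. At 40 per arm the standard error is 0.194 and power about 95%.
- The 95% interval multiplies and divides the ratio by exp(1.96 × 0.183) = 1.43. An estimated ratio of about 0.70 (1/1.43) is therefore borderline non-significant, and its interval reaches down to about 0.49 (0.70/1.43). Non-significance is still compatible with about half the oral level.
- The scale also changes the apparent answer. Geometric mean = mean/√(1 + CV²): 5.4/√1.269 = 4.79 for oral and 5.8/√3.571 = 3.07 for gel. The implied geometric ratio is 0.64, against an arithmetic ratio of 5.8/5.4 = 1.07.

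**5. What a margin would cost.** Take the 35% convention of Section 13.5.4 as a ratio margin of 0.65 to 1.54, with a true ratio of 1 and two one-sided 5% tests on the log scale. Power = 2Φ(ln(1/0.65)/SE − 1.645) − 1, which is about 52% at 45 per arm and 43% at 40.

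**The case against.** The strongest reply is that the intended analyte is obvious. Section 2.3.2 compares tissue and plasma (Z)-4-OHT in just this pattern, and Section 13.4.1 frames the breast hypothesis in terms of 4-OHT. On that reading Section 13.5.1 needs one word, and a difference test is right for tamoxifen and NDT. This stands as far as it goes and supports naming 4-OHT. It does not remove the conflict with Section 13.5.4, and it supplies no analysis that could support similarity.

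A second reply is that effectiveness is tested by Ki67, not by matched exposure. Section 2.3.2 reports tumour 4-OHT of 1.87 ng/g (gel, 2 mg/day) against 4.32 ng/g (oral) in invasive cancer, a ratio of 0.43, and still calls the Ki67 results roughly equal. That is fair and limits the severity.

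A reader might infer three stronger things that the documents do not support:
- That the trial is unable to show whether active exposure is matched. 4-OHT and endoxifen are both assayed in tissue and compared, so a shortfall in endoxifen would be visible. Only the pre-specified summary is missing.
- That the test breaks down when gel-arm tamoxifen or NDT is unquantifiable. Section 13.5.4 has a rank-test fallback, and no quantification limit is given.
- That the gel arm carries a known fraction of the oral arm's active drug. With equal 4-OHT, no gel-arm endoxifen and equal weights, the fraction is 1/(1 + r), where r is the oral-arm ratio of endoxifen to 4-OHT: 67% at r = 0.5, 25% at r = 3. The documents give no tissue endoxifen level, so r is assumed and this is illustration only.

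**Conclusion.** The point holds as an inconsistency between hypothesis and analysis for one secondary endpoint. At least two of the five listed analytes (tamoxifen and NDT) should not be expected to be similar, a third (endoxifen) is uncertain, and the test assigned to all five cannot support similarity for any of them.

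The size depends on the scale. On the raw scale a halved gel-arm 4-OHT level would be missed more often than not. On the log scale it would usually be found, but a non-significant result would still leave ratios down to about one half open. These figures rest on the SDs of one small trial, measured in adipose tissue, and on equal arms; the log-scale figures also assume log-normality.

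Severity is minor to moderate. The primary Ki67 analysis and its sample size are not affected.

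**What to change.** In Sections 13.5.1 and 13.5.4:
- Make the two sections agree on which analytes are expected to be similar and which to differ.
- Limit the tissue similarity hypothesis to 4-OHT, with (Z)-4-OHT as the key analyte and the (E) isomer also reported.
- Analyse it as a gel/oral geometric mean ratio with confidence interval. Fix the scale in advance and allow unequal variances, since the quoted SDs differ more than threefold (9.3/2.8 = 3.3).
- If similarity is to be concluded, state a justified margin beforehand. If power against it is as low as in step 5, report the ratio and interval as an estimate and draw no conclusion of similarity.
- State that tamoxifen and NDT are expected to differ in tissue, and report them descriptively.
- Report tissue endoxifen beside 4-OHT, with the molar sum of (Z)-4-OHT and (Z)-endoxifen as an optional supportive ratio with interval, so that matched 4-OHT is not read as matched active exposure.

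The cost is wording. Every analyte is already assayed, so no new sample or assay is needed. Section 10.3.2 ships the plasma and tissue for drug assay in one batch at study end, so the change can be made before any of these results exist.

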*cancer cells in situ equivalent to that of oral tamoxifen administered at the recommended dose of 20 mg/d.*

Pre-surgical Phase IIB study in women with DCIS (NWU 07-9-02) In a DCP-funded study, we confirmed equivalent reduction in Ki67 labelling of DCIS lesions by oral tamoxifen 20 mg and 4-OHT 2 mg/breast, in women treated for at least 6 weeks pre-operatively, see Figure 1 [35]. We also measured plasma levels of proteins involved in coagulation, and those reflecting systemic estrogenicity (serum IGF-1 and SHBG); we found the expected increases in the TAM group, but no significant changes in the 4-OHT gel group. Compliance was good and the gel was well-tolerated. The concentrations of (Z) 4-OHT in breast adipose tissue were equivalent in the two groups ( $5.4 \pm 2.8$  ng/g in oral TAM group and  $5.8 \pm 9.3$  ng/g in 4-OHT gel group,  $p=0.88$ ), but plasma (Z) 4-OHT concentrations were significantly lower in the gel group ( $1.1 \pm 0.7$  ng/mL vs.  $0.2 \pm 0.2$  ng/mL,  $p=0.0003$ ).

Mastalgia: A Phase 2 Study (01-4OHT-02) was conducted to assess the safety and efficacy of topical 4-OHT gel in treating cyclical mastalgia in pre-menopausal women [39], and tested 2-mg 4-OHT gel (n=40), 4-mg 4-OHT gel (n=39) or placebo (n=35) applied daily; 114 subjects were evaluated at 4-months. Those receiving 4 mg 4-OHT demonstrated statistically significant improvement in pain scores relative to placebo (-19.34 mm for placebo, -25.76 mm for 2-mg 4-OHT, and -32.06 mm for 4-mg 4-OHT). The gel was well tolerated at both doses. Mean plasma concentration of 4-OHT for the 2- and 4-mg treatment groups after 4 weeks (one month) of treatment were  $17 \pm 19$  pg/mL, and  $60 \pm 65$  pg/mL, while mean plasma levels following 16 weeks (4 months) of treatment were  $20 \pm 28$  pg/mL and  $50 \pm 64$  pg/mL, respectively [39]. The systemic exposure to 4-OHT following oral TAM administration of 20 mg/day has been reported to be between 2-6 ng/mL [30-32].

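### Breast-tissue drug levels are expected to be similar between arms but are assigned a test for difference, which cannot support that expectation

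*Combined protocol and SAP*

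**What the plan says.** Section 13.5.1, item 2, gives two different expectations for the drug-level endpoint: plasma should show "higher levels in the oral arm but tissue levels will be similar between arms".

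Section 13.5.4 describes two kinds of analysis, "noninferiority testing and testing for differences between arms, depending on the specific hypotheses for each outcome". Under the heading for treatment differences it then lists "Continuous endpoints for which treatment differences are expected post-treatment (breast and plasma levels of TAM and its metabolites" along with other markers, and these "will be compared between arms using a two-sample t-test". Normality is to be checked, a transformation such as the logarithm is allowed, and the Wilcoxon rank-sum test is the fallback. Among secondary efficacy outcomes, the non-inferiority paragraph names only the Oncotype DCIS-Score. Its margin is set "to correspond to a 35% change from the average baseline value observed among all patients".

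Section 10.2.1 limits drug concentration assays to Study Visit 1, the day of surgery.

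On the pilot trial, Section 2.3.2 states: "The concentrations of (Z) 4-OHT in breast adipose tissue were equivalent in the two groups". It gives 5.4 ± 2.8 ng/g (oral) and 5.8 ± 9.3 ng/g (gel), with p=0.88.

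**The concern.** By the plan's own rule, an outcome expected to be similar should not be placed with outcomes expected to differ. For tissue levels the rule is broken, and the assigned test can only reject equality or fail to reject it. If it fails, the trial has no planned basis for saying that tissue levels are similar, because no bound, between-arm ratio or interpretation rule is given.

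The margin rule for other secondary endpoints cannot fill the gap. It needs a baseline value, and drug levels have none.

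What is at stake is the tissue half of the pharmacological argument for local delivery, namely that the gel gives comparable breast exposure with low plasma exposure. Variable data make a non-significant result easier to obtain, and the pilot gel SD exceeds its mean.

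**Working it through.** **Plan's own figure.** No power, margin or sample-size calculation is given for tissue levels. The one stated power, 80.5% for the primary Ki-67 test (Section 13.4.2), reproduces: 2.6 / (5.4 × √(2/40)) = 2.153, and a noncentral t with 78 df at one-sided 0.10 gives 80.5%. It does not bear on tissue levels.

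**Inputs**
- Pilot tissue (Z) 4-OHT in breast adipose (Section 2.3.2): oral 5.4, SD 2.8; gel 5.8, SD 9.3 ng/g.
- Available for secondary endpoints (Section 13.2): 80 to 90 women, so n = 40 to 45 per arm.
- Assumptions: two-sided alpha 0.05 (Section 13.5.4 says two-sided but gives no level); lognormal concentrations for the log-scale results.

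**Log-scale parameters.** σ² = ln(1 + (SD/mean)²).
- Oral: SD/mean = 0.519, σ² = 0.238, σ = 0.49.
- Gel: SD/mean = 1.603, σ² = 1.273, σ = 1.13.

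**What the pilot figures imply.** Geometric mean = mean / √(1 + (SD/mean)²).
- Oral: 5.4 / 1.126 = 4.79. Gel: 5.8 / 1.890 = 3.07.
- Ratio gel/oral = 3.07 / 4.79 = 0.64.

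So near-equal arithmetic means are compatible with a typical gel user being about 36% lower.

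**Difference test, log scale.** SE = √((0.238 + 1.273)/n) = 0.194 (n = 40) or 0.183 (n = 45). Power = Φ(|ln ratio|/SE − 1.96).
- True ratio 0.65, |ln| = 0.431: Φ(0.26) = 60% and Φ(0.39) = 65%. Non-significant 40% and 35% of the time.
- True ratio 0.50, |ln| = 0.693: Φ(1.61) = 95% and Φ(1.82) = 97%; the noncentral t gives 94% and 96%. Non-significant about 3% to 6% of the time.

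**Difference test, raw scale.** SE = √((2.8² + 9.3²)/n) = 1.536 or 1.448 ng/g.
- 95% CI half-width: 3.06 or 2.88 ng/g, which is 57% or 53% of the oral mean.
- True 35% deficit (0.35 × 5.4 = 1.89 ng/g): power 23% or 25%, so non-significant 77% or 75% of the time.
- True 50% deficit (2.70 ng/g): power 41% or 45%.

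**Formal similarity test, log scale, true ratio 1.** Two one-sided tests at 0.05: power = 2Φ(ln(upper bound)/SE − 1.645) − 1.
- Bounds 0.70 to 1.43 (35/50 = 0.70, the retention used for Ki-67, and its inverse): 15% to 24%.
- Bounds 0.65 to 1.54: 43% to 52%.
- One-sided non-inferiority at 0.65 with alpha 0.10: 83% to 86%.

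All of these bounds are illustrations. The documents give none for tissue levels.

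**The case against.** The strongest reply has four parts.

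- **No rule of reading is stated.** A reader might infer that the plan will take p > 0.05 as similarity. No section says so. Section 13.5.4 plans descriptive statistics with confidence intervals and says the unadjusted tests will be interpreted accordingly. The word used for the pilot is background prose. This stands: the misreading is an inference, made likely by Section 2.3.2. The planned intervals are arm summaries, however, and no interval for the between-arm ratio or difference is specified.
- **The raw-scale power figures are too pessimistic.** A reader might conclude that a halving of tissue levels would be missed more than half the time. That holds only on the raw scale. With a gel SD above its mean, the planned normality check would probably lead to a log transformation, under which a 50% deficit is nearly always detected. This stands. The 35% to 40% miss rate for a 35% deficit remains.
- **Oral-like tissue levels are not the trial's key question.** Section 2.3.3 gives that place to achieving effective breast concentrations. Section 13.4.1 hypothesises breast levels above circulating levels, and the objective in Section 1.2 is to compare. This stands and limits the importance of the point. It does not remove the conflict between Sections 13.5.1 and 13.5.4.
- **A formal equivalence test would usually fail.** With bounds of 0.70 to 1.43 it would succeed only 15% to 24% of the time with identical arms, and those bounds borrow a Ki-67 ratio without justification for drug levels. This stands as an argument against requiring that test. It is no argument for leaving the difference test to carry a similarity hypothesis.

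**Conclusion.** The point holds as an internal conflict between hypothesis and test. Tissue levels are expected to be similar, the plan says the test follows the hypothesis, and the test assigned is for difference. A non-significant result would be weak evidence of similarity against a moderate deficit (35% missed about 35% to 40% of the time on the log scale, about 75% to 77% on the raw scale). It would be much stronger evidence against a 50% deficit on the log scale.

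These sizes rest on one analyte in adipose tissue from a trial that enrolled 28 women, on a lognormal shape, and on an assumed alpha of 0.05. The implied ratio of 0.64 shows what equal arithmetic means can hide. It is not an estimate that the gel falls short.

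The conflict does not cover every analyte equally. The gel delivers 4-OHT, itself a tamoxifen metabolite, so a difference test for tissue tamoxifen and N-desmethyl tamoxifen is reasonable. The endpoint is secondary and the Ki-67 conclusion does not depend on it.

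**What to change.** In Section 13.5.4:

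- Separate tissue from plasma levels, and keep the difference test for plasma.
- Name the analyte expected to be similar. Tissue (Z) 4-OHT is the natural choice, as it was the pilot comparison. State the hypothesis for tissue tamoxifen and N-desmethyl tamoxifen separately.
- For that analyte, analyse log concentration and report the gel/oral geometric mean ratio with a confidence interval.
- State that p > 0.05 will not be taken as evidence of similarity.
- Let any claim of similarity or non-inferiority rest on a bound for the ratio, justified and fixed before unblinding. If none can be justified, report the ratio and interval descriptively.

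The cost is SAP wording, with no new data or samples. The downside is that two-sided equivalence is unlikely to be shown at this sample size. At 40 per arm, and taking the pilot SDs, the 95% interval would run from the estimated ratio divided by about 1.46 to the ratio multiplied by the same factor (exp(1.96 × 0.194) = 1.46).
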